| | At baseline visit, subjects will receive the study acne device to be applied to the areas of the face afflicted by acne following cleansing, every other day. The dermatologist investigator will assess the face for the investigator global acne assessment (IGA) based on the following 5 point ordinal scale: 0=clear, 1=almost clear, 2=mild, 3=moderate, and 4=severe. In addition, the dermatologist investigator will perform |

an inflammatory and non-inflammatory lesion count. The dermatologist investigator will assess the tolerability of the device in terms of peeling, dryness, redness, and swelling on a 5-point ordinal scale (0=none, 1=minimal, 2=mild, 3=moderate, & 4=severe).

The subjects will assess device tolerability in terms of itching, burning, redness, and swelling. All assessments will be made on a 5-point ordinal scale (0=none, 1=minimal, 2=mild, 3=moderate, & 4=severe). Subjects will be given their diaries, study device, and electroconductive media and asked to return to the research center in 2 weeks. A reminder text will be sent to encourage compliance prior to the week 2 visit.

Subjects will return to the research center at week 2, week 4, and week 8 for the same study activities as conducted at baseline. However, in addition a subject self-assessment marketing questionnaire provided by the sponsor will be administered. Subject diaries will be checked at each return visit for compliance and completion. Subjects will be re-dispensed electroconductive media as needed at each visit; and the devices will be inspected for continued functionality. Reminder texts will be sent prior to each visit to encourage compliance.

Subjects will return to the research center at week 12 for the same study activities as conducted at baseline. Study diaries and devices will be checked and collected. Subjects will terminate their study participation at this time.

All investigator selected subjects will be photographed with the Canfield VISIA CR using Standard 1 lighting at baseline, week 2, week 4, and week 8, and week 12.

Subjects will be provided with the following device instructions:

- 1. Begin with clean, dry skin.
- 2. Inspect your skin and identify which zones of your face have acne. The four facial zones are divided as follows: 1) Upper Left, 2) Upper Right, 3) Lower Left, and 4) Lower Right. The zone(s) identified now will be treated throughout the study.
- 3. Liberally apply the conductive gel provided to you over each zone which has acne.

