- 4. Turn on your device by pressing the button at the top. You will hear one beep.
- 5. Place the device on your skin. Lights will illuminate under the device when both silver probes come in contact with your skin. Both probes must keep contact with skin throughout treatment.
- 6. Slowly make continuous circles with the top probe (the one farthest away from the charging port) over acne within each facial zone. (You may feel a tingling sensation during treatment. That is normal.)
- 7. Treat each facial zone for 1 minute. Your device will beep and vibrate at the one minute mark to indicate that treatment of that zone is complete. Only treat the acne zone(s) identified for treatment.
- 8. At the end of treatment, your device will beep twice and turn off.

- 9. After treatment, wipe your device clean with a tissue, being careful to avoid the charging port. Spray the device and a second tissue lightly with rubbing alcohol and wipe again, remaining careful to avoid the charging port.
- 10. Store safely away from water, moisture or debris. After treatment, wipe your device clean with a tissue before putting it away.
- 11. Repeat treatment of the original acne zone(s) through the study. Perform treatments every other day for 12 weeks.
- 12. If any new areas of acne develop later in the study, you may also treat those additional zones until study completion. For example, if you have acne in the forehead and mouth zones at the start of the study, treat those two zones for every treatment. If additional acne develops on the left cheek later in the study, treat the left cheek zone in addition to the mouth and forehead zones for all remaining treatments

CHARGING:

When you see the orange light flashing while using your device, it's time to charge. To charge, plug in the charging cable provided. The orange light will remain illuminated while charging. You will know that your device is completely charged when the orange light is no longer on.

CONTRAINDICATIONS

ZIIP should not be used in the following areas

- Breast area
- Directly on top of the eyelid
- Midline of neck (bone of neck)
- Groin area
- Do not use this device on patients who have a cardiac pacemaker, implanted defibrillator, or other implanted metallic or electronic device because this may cause electric shock

WARNINGS

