10.2 PRECAUTIONS

Study products should be used as instructed and not orally consumed or placed in the eyes or around the orbital area of the eye. The device should be used as described below:

- 1. Begin with clean, dry skin.
- 2. Apply the conductive medium provided to you liberally over any areas where you have acne.
- 3. Turn on your device by pressing the button at the top. You will hear one beep.
- 4. Place the device on top of your skin. Lights will illuminate under the device when both silver probes come in contact with your skin. Both probes must keep contact with skin throughout treatment.
- 5. Follow along with the video, slowly making circles with the top probe (the one farthest away from the charging port) over acne within each zone. (You may feel a tingling sensation during treatment. That is normal.)
- 6. Do not treat a single spot more than one minute at a time. Only treat the facial zones identified for treatment.
- 7. At the end of treatment, your device will beep twice and turn off.
- 8. After treatment, wipe your device clean with a tissue, being careful to avoid the charging port. Spray the device and a second tissue lightly with rubbing alcohol and wipe again, remaining careful to avoid the charging port.
- 9. Store safely away from water, moisture or debris.

CHARGING:

When you see the orange light flashing while using your device, it's time to charge.

To charge, plug in the charging cable provided. The orange light will remain illuminated while charging. You will know that your device is completely charged when the orange light is no longer on.

CONTRAINDICATIONS

ZIIP should not be used in the following areas

- Breast area
- Directly on top of the eyelid
- Midline of neck (bone of neck)
- Groin area
- Do not use this device on patients who have a cardiac pacemaker, implanted defibrillator, or other implanted metallic or electronic device because this may cause electric shock

WARNINGS

Do not submerge the device in water or any other liquid(s). If you store your ZIIP in an area such as a bathroom counter, ensure the product does not come in contact with water or other liquid(s).

ZIIP should not be used by:

- Children
- Pregnant Women
- People subject to seizures
- People with cancer/tumors

- People with a cardiac pacemaker
- People with implanted defibrillators/stimulators
- People with electronic implanted devices

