10.3 STUDY PRODUCT ADMINISTRATION

Subjects will use the acne device for applied 3 days per week on non-consecutive days, on all facial zones afflicted by acne. The electroconductive media will be applied to the face prior to the use of the device. The following instructions will be provided:

- 1. Both silver probes must come in contact with skin throughout treatment.
- 2. Slowly make continuous circles with the top probe (the one farthest away from the charging port) over acne within each facial zone.
- **NOTE: Instructional video will be provided for participants to follow**
- 3. Treat each facial zone for 1 minute. Your device will beep and vibrate at the one minute mark to indicate that treatment of that zone is complete. Only treat the acne zone(s) identified for treatment.
- 4. After treatment, wipe your device clean with a tissue, being careful to avoid the charging port. Spray the device and a second tissue lightly with rubbing alcohol and wipe again, remaining careful to avoid the charging port.
- 5. Store safely away from water, moisture or debris.

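### The device instructions define four quadrant zones, but their worked example counts forehead, mouth and left cheek as zones, so time at one minute per zone may differ between subjects with the same acne

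*Combined protocol and SAP*

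**What the plan says.** The numbered device instructions in the synopsis (section 1) are what subjects follow at home. Instruction 2 asks subjects to identify which zones have acne and gives a closed definition: "The four facial zones are divided as follows: 1) Upper Left, 2) Upper Right, 3) Lower Left, and 4) Lower Right". It adds: "The zone(s) identified now will be treated throughout the study".

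Time is set per zone. Instruction 7, the device row of the synopsis and section 10.3 all state the rule: "Treat each facial zone for 1 minute".

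Instruction 12 allows zones to be added if acne appears elsewhere, and illustrates this: "if you have acne in the forehead and mouth zones at the start of the study, treat those two zones for every treatment". If acne later develops on the left cheek, the subject is to "treat the left cheek zone in addition to the mouth and forehead zones for all remaining treatments".

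Section 7.2.1 has the investigator count lesions by quadrant and glosses quadrant as zone. Sections 7.2.2 to 7.2.5 count by quadrant at every later visit.

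**The concern.** Forehead, mouth and left cheek are not among the four defined zones, yet the example calls them zones and counts the first two as two. The definition and the example sit in one list, and no section translates between them.

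Since each zone receives one minute, the number of zones sets the length of a session. Two subjects with identical acne could both follow the sheet in good faith and treat for different times, one counting quadrants and the other counting facial regions. This is a single-arm study with treatment at home, so the written instructions are a main control on exposure. If they can be read in two ways, the treatment time behind the result cannot be described consistently.

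**Working it through.** **Inputs**

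- Time per zone: 1 minute (synopsis instruction 7; section 10.3).
- Scheme A: four quadrants (synopsis instruction 2; section 7.2.1).
- Scheme B: forehead, mouth and left cheek as separate zones (synopsis instruction 12).
- Sessions: three per week for 12 weeks gives 3 × 12 = 36 (sections 7.1.5 and 10.3). Every other day over 84 days gives 84 / 2 = 42 (synopsis instruction 11). The two frequencies are a separate inconsistency. They change the totals below but not the ratios.
- Assumptions, not stated in the documents: which side of the face is affected; that forehead acne falls in the upper quadrants and mouth acne in the lower; and, for the last row of the table only, that the affected part of the left cheek lies in the upper left quadrant.

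The plan states no treatment time per session, so there is no figure of its own to reproduce.

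**Formula:** minutes per session = number of zones × 1 minute; ratio = scheme A / scheme B.

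| Acne pattern | A: quadrants (min) | B: example's zones (min) | Ratio A/B |
|---|---|---|---|
| Forehead and mouth, both sides | 4 | 2 | 2.0 |
| Forehead only, both sides | 2 | 1 | 2.0 |
| Mouth only, both sides | 2 | 1 | 2.0 |
| Forehead one side, mouth both sides | 3 | 2 | 1.5 |
| Forehead and mouth both sides, plus left cheek | 4 | 3 | 1.33 |
| Forehead and mouth, one and the same side | 2 | 2 | 1.0 |
| Left forehead and left cheek, all in the upper left quadrant | 1 | 2 | 0.5 |

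**Cumulative time, first row**

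- 36 sessions: 4 × 36 = 144 minutes against 2 × 36 = 72 minutes.
- 42 sessions: 4 × 42 = 168 minutes against 2 × 42 = 84 minutes.

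**Can the example be loose wording for quadrants?** If the forehead and mouth acne crosses the midline, it cannot. All four quadrants are then already under treatment, and no zone is left for the left cheek to add. If all the acne is on the right, left-cheek acne would add a quadrant, but the new zone would then be a left quadrant, not one called left cheek. Either way the example's labels come from a different scheme.

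**The case against.** The best defence is that one illustrative example is a leftover and the working definition is clear. Instruction 2 is explicit, section 7.2.1 repeats it, first use is supervised at the research center, a video is provided, and diaries are checked at each return visit. This has weight: the documents support only that subjects may treat differently, not that they will. It does not close the point, because neither the supervised session nor the video is said to teach a particular scheme, and the written example still contradicts the definition.

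It can also be said that session time already varies by design from 1 to 4 minutes with the number of affected quadrants, and that the efficacy endpoint in section 12.5 is the IGA. Both are true. The ambiguity adds variation unrelated to the extent of acne, but it does not prevent the IGA comparison.

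A reader might infer several stronger points that the documents do not support:

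- *That instruction 7 conflicts with instruction 12.* Instruction 7 says "Only treat the acne zone(s) identified for treatment", and instruction 12 expressly extends the set of identified zones. This is a rule with an extension.
- *That section 10.2 conflicts with section 10.3.* Section 10.2 says "Do not treat a single spot more than one minute at a time". A ceiling per spot is compatible with a minute per zone, and section 10.3 supplies the zone rule.
- *That zone counts in the diaries will not be comparable.* Section 8.1 has subjects record use of the device and the medium, with comments. It does not say that zones are recorded.
- *That a planned analysis fails because treated zones do not match the lesion-count quadrants.* Section 12 plans no analysis by treated zone or by exposure.

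**Conclusion.** The inconsistency is real and lies within one set of subject instructions. It is more than a labelling slip, because the zone count sets the treatment time.

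The largest difference among the patterns worked through is twofold, 4 against 2 minutes per session. It assumes forehead and mouth acne on both sides of the midline. The ratio is not general: it runs from 0.5 to 2.0 across those patterns, and its direction can reverse. The effect is therefore inconsistent exposure, not a uniform excess or shortfall. How many subjects would follow each scheme cannot be judged from the documents.

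A reader might go further and infer that the trial's result cannot be interpreted at all. That goes too far: the IGA comparison with baseline stands as planned. What is weakened is a consistent statement of the treatment time behind it. The point should be corrected before enrolment, but it does not threaten the efficacy endpoint.

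**What to change.** Reconcile the synopsis (device row and instructions 2, 7 and 12), sections 7.2.1 and 10.3, the subject handout and the video, so that the definition and the worked example use one zone scheme. Rewrite the example in the labels of that scheme. Which scheme applies is for the sponsor and investigator to decide; this review takes no view on it or on the treatment time.

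Have the diary record which zones were treated at each session, using the labels on the lesion-count form, so that the exposure actually delivered can be described.

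The cost is a text correction, a check of the video and one added diary field, all before the first subject is enrolled. No change to the sample size, visits or analysis is needed.

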1. PROTOCOL SYNOPSIS

| Title of Study: | Evaluation of the Safety and Efficacy of an Acne Treatment Device |
|--|---|
| Study Period: | 12 weeks |
| Test Device and Application Instructions: | ZIIP Device (active) -400 microamps direct current, applied 3 days per week on non-consecutive days, on all areas afflicted by acne The following instructions will be provided: 1. Both silver probes must come in contact with skin throughout treatment. 2. Slowly make continuous circles with the top probe (the one farthest away from the charging port) over acne within each facial zone. **NOTE: Instructional video will be provided for participants to follow** 3. Treat each facial zone for 1 minute. Your device will beep and vibrate at the one minute mark to indicate that treatment of that zone is complete. Only treat the acne zone(s) identified for treatment. 4. After treatment, wipe your device clean with a tissue, being careful to avoid the charging port. Spray the device and a second tissue lightly with rubbing alcohol and wipe again, remaining careful to avoid the charging port. 5. Store safely away from water, moisture or debris. |
| Ancillary Product and Application Instructions: Objective: | Electroconductive Media Apply as a thin layer to all facial areas afflicted with acne The objective of this study is to demonstrate the safety and efficacy of a novel direct |
| Objective. | current device employed in the treatment of mild to moderate inflammatory acne after 12 weeks of every other day use. |
| Design: | Male and female subjects will be enrolled in this single-site monadic study to evaluate the effect of a device on acne treatment. Subjects who sign the consent form and meet all inclusion criteria and none of the exclusion criteria will be enrolled at the baseline visit. Subjects will be asked to continue use of their self-selected moisturizer, non-medicated cleanser, and sunscreen they have used without difficulty for the prior 30 days and for the 12-week study. Subjects must also continue all facial products and cosmetics unchanged for the duration of the study. No other oral or topical acne products can be used. Subjects must be washed out of all topical acne products for at least 2 weeks and all oral acne products for at least 4 weeks prior to study participation. Subjects must possess mild to moderate acne with 5-30 inflammatory lesions and no nodules/cysts. |

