Do not submerge the device in water or any other liquid(s). If you store your ZIIP in an area such as a bathroom counter, ensure the product does not come in contact with water or other liquid(s).

ZIIP should not be used by:

- Children
- Pregnant Women
- People subject to seizures
- People with cancer/tumors
- People with a cardiac pacemaker
- People with implanted defibrillators/stimulators
- People with electronic implanted devices

If you have any medical concerns, such as a severe medical illness, epilepsy or seizures, or recent facial surgery, please consult your doctor before using ZIIP.

| DΔ | GF | Q S | αf | 28 |
|----|-------------|------|------------|----|
| | · · · · · · | · () | ()1 | ~0 |

| Dermatology Consulting Services, PLLC | Dermatol | logy C | Consulting | Services. | PLLC |
|---------------------------------------|----------|--------|------------|-----------|------|
|---------------------------------------|----------|--------|------------|-----------|------|

| | Electronic monitoring equipment (such as ECG monitors and ECG alarms) may not operate properly when a ZIIP device is in use. |
|-------------|---|
| | Stimulation should not be applied over, or in proximity to cancerous lesions, or applied over swollen, infected, or inflamed areas or skin eruptions, e.g., phlebitis, thrombophlebitis, broken capillaries, varicose veins, etc. Men should shave before use as hair can interfere with the conductivity of the electrodes. Facial area under a beard or mustache cannot be treated. |
| | Do not apply stimulation across your chest as the introduction of electrical current into the chest may cause rhythm disturbances to your heart, which could be lethal. |
| | The long-term effects of stimulation are not known. |
| | (There is an allowance for an unscheduled visit at any time, if necessary.) |
| Study | Healthy male and female subjects 18-50 years of age of all Fitzpatrick skin types |
| Population: | with mild to moderate acne consisting of 5-30 inflammatory lesions and no nodules/cysts. |
| Number of | 50 subjects |
| Patients: | |
| Inclusion | 1. Subjects with mild to moderate acne (5-30 inflammatory lesions and no |
| Criteria: | nodules/cysts). |
| | 2. Male and female subjects age 18-50 years. |
| | 3. Subjects with all Fitzpatrick skin types. |
| | 4. Subjects of all complexion types (normal, oily, dry, combination). |

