- 10. Subjects who have a history of a psychological illness or condition that would interfere with their ability to understand and follow the requirements of the study.
- 11. Subjects who have undergone recent facial surgery.
- 12. Subjects currently participating in any other clinical trial.
- 13. Subjects having started hormone replacement therapies (HRT) or hormones for birth control less than 3 months prior to the study entry; or who plan on starting, stopping or changing doses of HRT or hormones for birth control during the study.
- 14. Subjects who have a cardiac pacemaker, implanted defibrillator, or other implanted metallic or electronic device.
- 15. Subjects who are wearing EKG monitoring equipment.
- 16. Subjects with phlebitis, thrombophlebitis, broken capillaries, or varicose veins.
- 17. Subjects who have seizures, epilepsy, or cancer/tumors.
- 18. Subjects who have a history of hypertrophic scarring or keloid formation.

Endpoints:

Tolerability Endpoint:

The tolerability endpoint is the investigator-assessed absence of skin irritation from the facial study device at any time during the 12-week study.

Safety Endpoint:

The safety endpoint is the overall incidence of all adverse events reported during the study.

Efficacy Endpoint: The efficacy endpoint is the investigator assessed improvement in investigator global assessment (IGA) after 12 weeks of every other day device use as compared to baseline.

Measures:

Dermatologist Investigator assessed efficacy parameters: Investigator global acne assessment (IGA) based on the following 5 point ordinal scale: 0=clear, 1=almost

clear, 2=mild, 3=moderate, and 4=severe. IGA assessments will be conducted at baseline, week 2, week 4, week 8, and week 12.

Dermatologist Investigator lesion counts: inflammatory lesion count (papules, pustules), non-inflammatory lesion count (open comedones, closed comedones). Lesion counts will be conducted at baseline, week 2, week 4, week 8, and week 12.

Dermatologist Investigator assessed tolerability parameters: peeling, dryness, redness, and swelling. All assessments will be made on a 5-point ordinal scale (0=none, 1=minimal, 2=mild, 3=moderate, & 4=severe) at baseline, week 2, week 4, week 8, and week 12.

Self-assessment questionnaire: To be provided by sponsor. All assessments will be at week 2, week 4, and week 8, and week 12.

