4. STUDY OBJECTIVE

The objective of this study is demonstrate the safety and efficacy of a novel direct current device in the treatment of mild to moderate inflammatory acne after 12 weeks of every other day use.

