6.3 INCLUSION CRITERIA

The following items represent the inclusion criteria:

- 1. Subjects with mild to moderate acne (5-30 inflammatory lesions and no nodules/cysts).
- 2. Male and female subjects age 18-50 years.
- 3. Subjects with all Fitzpatrick skin types.
- 4. Subjects of all complexion types (normal, oily, dry, combination).
- 5. Subjects who have used the same moisturizer without difficulty for 30 days and will continue using same moisturizer during the 12 week study.
- 6. Subjects agree not to introduce any new colored cosmetics (lipsticks, eye shadows, facial foundations, blush, & powder).
- 7. Subjects who are using no other acne products for the duration of the study.
- 8. No known medical conditions that, in the investigator's opinion, may interfere with study participation.
- 9. Women of childbearing potential must be willing to use a form of birth control during the study. For the purpose of this study, the following are considered acceptable methods of birth control: oral contraceptives, Norplant®, Depo-Provera®, double barrier methods (e.g., condom and spermicide) and abstinence.
- 10. Subjects have signed an Informed Consent Form in compliance with 21CFR, Part 50: "Protection of Human Subjects."
- 11. Subjects are dependable and able to follow directions and willing to comply with the schedule of visits.

12. Subjects in generally good physical and mental health.

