6.4 EXCLUSION CRITERIA

The following items represent the exclusion criteria:

- 1. Any dermatological disorder, which in the investigator's opinion, may interfere with the accurate evaluation of the subject's skin characteristics, except for the study condition of acne.
- 2. Subjects who are not willing to use the assigned study device to their face as instructed.
- 3. Subjects who have used any topical prescription or OTC acne products for 2 weeks prior to study entry.
- 4. Subjects who have taken any oral prescription or OTC acne products for 4 weeks prior to study entry.
- 5. Subjects who have used a non-OTC cleanser without benzoyl peroxide, sulfur or salicylic acid for at least 2 weeks prior to study entry.
- 6. Subject who have not had any facial treatments in the past 6 months and are willing to withhold all facial treatments during the course of the study including facials, facial peels, photo facials, laser treatments, dermabrasion, botulinum toxin (Botox), injectable filler treatments, intense pulsed light (IPL), acid treatments, tightening treatments, and/or facial plastic surgery.
- 7. Subjects who are pregnant, breast feeding or planning a pregnancy.
- 8. Subjects with clinically significant and/or unstable medical disorders.
- 9. Subjects who are unwilling or unable to comply with the requirements of the protocol.
- 10. Subjects who have a history of a psychological illness or condition that would interfere with their ability to understand and follow the requirements of the study.
- 11. Subjects who have undergone recent facial surgery.
- 12. Subjects currently participating in any other clinical trial.
- 13. Subjects having started hormone replacement therapies (HRT) or hormones for birth control less than 3 months prior to the study entry; or who plan on starting, stopping or changing doses of HRT or hormones for birth control during the study.
- 14. Subjects who have a cardiac pacemaker, implanted defibrillator, or other implanted metallic or electronic device.
- 15. Subjects who are wearing EKG monitoring equipment.
- 16. Subjects with phlebitis, thrombophlebitis, broken capillaries, or varicose veins.
- 17. Subjects who have seizures, epilepsy, or cancer/tumors.
- 18. Subjects who have a history of hypertrophic scarring or keloid formation.

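### Subjects are told to move the probe over acne and also warned not to stimulate inflamed areas or skin eruptions, with no exemption for the acne being treated

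*Combined protocol and SAP*

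**What the plan says.** **Where to apply the device.** The synopsis gives the instruction twice, under the test device (step 2) and in the subject instructions (step 6): "Slowly make continuous circles with the top probe (the one farthest away from the charging port) over acne within each facial zone". Section 10.3, step 2, repeats it. Section 10.2, step 5, has the equivalent, "slowly making circles with the top probe (the one farthest away from the charging port) over acne within each zone", in a list introduced by "The device should be used as described below".

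**Where not to apply it.** The Warnings text, in the synopsis and again in section 10.2, says stimulation should not be applied over or near cancerous lesions, or "applied over swollen, infected, or inflamed areas or skin eruptions, e.g., phlebitis, thrombophlebitis, broken capillaries, varicose veins, etc".

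**What is being treated.** Section 4 states the objective as "treatment of mild to moderate inflammatory acne after 12 weeks" of use. Section 6.3, item 1, admits "Subjects with mild to moderate acne (5-30 inflammatory lesions and no nodules/cysts"). The synopsis (Measures) defines the "inflammatory lesion count (papules, pustules").

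**The concern.** The protocol calls its own target inflamed. An inflamed papule or pustule falls within the ordinary meaning of an inflamed area or a skin eruption, so the warning as worded covers the lesions that the instructions tell subjects to treat. Either the study procedure conflicts with a stated warning, or the warning is wrong for this use. The documents do not say which.

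Two things are at stake. The first is what subjects are told about safe use, because the synopsis places the instructions and the warning together in material for subjects who will treat themselves at home for 12 weeks. The second is what the efficacy data mean. A subject who heeds the warning could leave target lesions untreated and still record that the device was used. The week 12 IGA and the inflammatory lesion counts could then mix treated and avoided lesions, with no record of which were which.

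**Working it through.** The plan states no figure on this point, and the check involves no alpha, power or effect size. It compares texts.

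**Step 1. Set the statements side by side.**

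| Content | Where it stands | Count |
|---|---|---|
| Move the probe over acne | Synopsis, test device, step 2; synopsis, subject instructions, step 6; section 10.2, step 5; section 10.3, step 2 | 4 |
| Do not stimulate inflamed areas or skin eruptions | Synopsis, Warnings; section 10.2, Warnings | 2 |
| Exemption of acne from that warning | Not found in the text reviewed | 0 |

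The synopsis and the body repeat each other, so this is one conflict stated several times, not several conflicts.

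**Step 2. Does the warning's wording reach acne?** Its general terms are inflamed areas and skin eruptions. The four examples are vascular, but they are introduced as examples and the list is left open at the end. The protocol's own definition of an inflammatory lesion (papules and pustules) fits the general terms.

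**Step 3. Is acne exempted elsewhere?** The only exception for acne is in section 6.4, exclusion 1. It concerns skin disorders that could interfere with evaluation and does not address where current may be applied. Exclusion 16, "Subjects with phlebitis, thrombophlebitis, broken capillaries, or varicose veins", takes up the four examples but not the general terms. Section 7.1.5 says the device is customised for acne and leaves the warning unmodified.

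**Step 4. How far does it reach?** The inputs are 50 subjects (section 6.1) and 5 to 30 inflammatory lesions each at entry (section 6.3).

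- Minimum: 50 × 5 = 250 lesions
- Maximum: 50 × 30 = 1,500 lesions

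This shows how many lesions fall under both texts at baseline. It does not measure harm or bias.

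**Step 5. Would the data reveal avoidance?** Under section 8.1 the diary takes device and media application plus free comments. The schedule in section 2 has it checked at weeks 2, 4, 8 and 12. No entry for lesions or areas skipped is described. Lesion counts are made by facial quadrant (section 7.2), which would not separate treated from avoided lesions within a zone.

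**The case against.** The best case for the plan is that the warning is general device labelling never meant to cover acne. All its examples are vascular, and exclusion 16 already removes subjects with those conditions. Much of the rest of the warning text also has its own eligibility rule: pregnancy, implants, ECG monitoring, seizures, cancer and recent facial surgery. The same text mentions the breast, groin and chest, which have no bearing on a facial study. Section 7.1.5 describes the marketed device customised for acne, so the acne-specific instruction could be taken to govern. This reading is plausible, but it is stated nowhere, and the open-ended list does not support it. If the warning is carried-over text, it still needs to be reconciled with this use.

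A second objection is that avoidance is unlikely. First use is supervised at the centre (section 7.2.1), a video is provided, exclusion 2 removes those unwilling to use the device as instructed, and each zone is treated in a timed one-minute pass. These measures do make it likely that most subjects will treat their lesions. They do not change the written warning. It is also fair that a diary of device use would not normally log single lesions. The diary matters here only because it could not be relied on to show avoidance.

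A third objection is that the lead-in in section 10.2 introduces the numbered steps, while the warnings follow under their own heading. That is correct, so little weight should rest on the shared lead-in. The conflict does not depend on it.

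**Conclusion.** The concern holds. As written, the instruction and the warning cannot both be followed on an inflamed acne lesion, and every eligible subject has such lesions: 50 subjects, with 250 to 1,500 lesions at baseline. It should be fixed before enrolment.

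Confidence is high that the texts conflict. It is lower that subjects would act on the warning, and the size of any effect on safety or efficacy cannot be estimated from the documents. The conflict shows unclear text and is not itself evidence that the device is unsafe on acne.

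The conclusion assumes the warning's general terms carry their ordinary meaning. The absence of an exemption is confirmed only for the text reviewed. The consent pages, the diary form and the video were not available. Clarification there would bear on how subjects behave, but would not cure the protocol wording.

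**What to change.** Before enrolment, the sponsor and investigator should reconcile the device instructions and the Warnings text in the synopsis, section 10.2 and section 10.3. The protocol, the subject instructions and the video should then carry one consistent statement on use over inflamed acne lesions. Which rule is right is a clinical matter for them, and this review takes no position on it.

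The cost is a wording amendment with written sponsor and IRB approval under section 14.5, and a check of the video against the agreed wording, with correction if it differs. No visits or procedures are added. The title pages describe the protocol as ready for IRB submission with run dates still to be set, so the change can be made in time.
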